2. Study timeline. Year 1 will include start-up tasks and initiating the pilot trial. Year 2 will involve completing the pilot trial, cleaning and analyzing data, and preparing manuscripts and the RR&D IIR RCT proposal to test TEE efficacy (see Table 1).

Table 1. Study Timeline.

Activities	Year 1				Year 2			
	Q1	Q2	Q3	Q4	Q1	Q2	Q3	Q4
IRB	X	X						
Hire and train RA	X	X						
Develop AC	X	X						
Develop TEE and AC fidelity measure		X	X					
Recruit participants/provide TEE & AC		X	X	X				
Complete assessments		X	X	X	X			
Enter and clean data		X	X	X	X	X		
Analyze data					X	X		
Present findings						X	X	
Prepare manuscript and RR&D IIR RCT						X	X	

3. Setting. All research procedures will be conducted at VA Connecticut West Haven and Newington campuses. TEE and AC will be delivered off-site at the TEE location in Sharon, CT.

4. Participant eligibility criteria. Inclusion criteria for Veterans are: 1) seeing a VACHS mental health clinician at least three times in the past 3 months with intent to remain in treatment during study enrollment; 2) age 18 and over; 3) social dysfunction (score \geq 2.5 on the Social Adjustment Scale—Self-Report or \geq 1.5 on the Inventory of Interpersonal Problems—32); 4) emotion dysregulation (score \geq 95 on Difficulties in Emotion Regulation Scale); and 5) consent to all study procedures, including audio recording of group intervention sessions. Exclusion criteria are: 1) psychotic disorder as self-reported by the Veteran and verified in the electronic health record or as determined by the Mini-International Neuropsychiatric Interview; 2) acute suicidality, 3) inability to read English or communicate in spoken English; 4) anticipated unavailability to the study during the next 16 weeks; 5) participation in any EFT in the past 24 weeks; and 6) unavailability of a landline or cellular telephone. Clinicians are eligible for study participation if 1) they have seen one of the Veteran participants assigned to TEE at least three times in the past 3 months at the participant's baseline assessment, and 2) this Veteran received at least one TEE session and one psychotherapy/counseling session with the clinician prior to the key informant interview.

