Direct-to-participant and clinician recruitment will occur via flyers, visits to clinic rounds, and email to clinicians at VA Connecticut sites, including Vet Centers in Connecticut. The study also will be presented to Veterans during community meetings at Errera Community Care Center programs located in West Haven and Newington. In addition, clinicians and peer specialists will be provided with study cards that they can hand to Veterans if they feel the Veterans might be appropriate for study participation. If Veteran participants have more than one mental health clinician, they will be asked to identify which clinician they see as primarily providing them mental health psychotherapy/counseling, and the research assistant will invite that person to participate in the study. The decision of Veterans' clinicians to enroll in the study will not affect potential Veteran participants' study eligibility, particularly because their clinicians will be approached for study participation after Veterans have already enrolled. The PI, project coordinator, and Co-Is will have monthly meetings to review the number of individuals assessed for eligibility and those who were found ineligible (with reasons), declined to participate (with reasons), randomized, started, completed, withdrew, and completed assessments at each timepoint. Quarterly/semi-annual reports of these numbers will be provided to the Data Safety Monitoring Board (DSMB).

7. Screening. We will seek waivers of written informed consent and HIPAA authorization for an initial phone screening. The research assistant (RA) will offer Veterans information about the study and invite interested parties to complete a brief phone screening on quickly obtained eligibility criteria (e.g., if they have received EFT in the past 6 months). Individuals who remain eligible will next attend an in-person meeting in which to learn more about the study in detail, including completing an additional screening to further determine inclusion and exclusion criteria (e.g., completion of psychiatric interview, social functioning, and emotion dysregulation assessments). If the potential participant is agreeable, the RA will invite individuals to provide written informed consent and then will complete the screening to determine eligibility. Only individuals who meet eligibility criteria will be invited to continue in the study and participate in the baseline assessment.

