	Experiential learning activity	Collaboration/ grooming, hooking up with horse in round pen	Team building activity requiring communication in pairs

9. Assessments. Assessments will occur at screening, baseline, 4- and 16-weeks post-randomization. [name] will train the RA (blind to condition) to administer assessments. Assessments will be conducted either in-person or remotely, depending on COVID-19 pandemic conditions and the participants' preference. As with the screening process, if conducted in-person, research staff and participants will be required to wear a 2-ply face mask during study visits and social distance. If the participants do not have a mask, one will be provided for them. Research staff will sanitize the office between each in-person visit and at the end of the day. If conducted remotely, research staff will use either phone or a VA-approved video conference platform. Assessment sessions, regardless of mode of delivery, will not be recorded. The RA will schedule assessment sessions. Veterans will be instructed to not tell the RA their intervention assignments.

Sample description. Demographics will be assessed with the 15-item Phen-X adult Demographic protocol. Military demographics and experiences will be assessed with the 11-item Phen-X Military Service Demographics measure. The Mini-International Neuropsychiatric Interview³⁰ will assess psychiatric diagnoses.

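### The research assistant declared blind to condition is the only named inviter of clinicians, who qualify only through a TEE-assigned Veteran, and the plan does not say how the blind is kept

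*Combined protocol and SAP*

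**What the plan says.** All references are to the combined protocol and SAP.

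- **Section 9 (Assessments), the blind.** A team member "will train the RA (blind to condition) to administer assessments". The same paragraph adds "The RA will schedule assessment sessions" and "Veterans will be instructed to not tell the RA their intervention assignments".
- **Section 6 (Recruitment and feasibility), the invitation.** The sentence begins "If Veteran participants have more than one mental health clinician, they will be asked to identify which clinician" is their main provider of psychotherapy or counseling, and ends "the research assistant will invite that person to participate in the study". On timing, the section says only that "their clinicians will be approached for study participation after Veterans have already enrolled".
- **Section 4 (Participant eligibility criteria), who qualifies.** Clinicians are eligible if "they have seen one of the Veteran participants assigned to TEE at least three times in the past 3 months" before that Veteran's baseline, and if "this Veteran received at least one TEE session and one psychotherapy/counseling session with the clinician prior to the key informant interview".
- **Section 5 (Randomization).** The project coordinator carries out randomization. Nothing gives that role the clinician invitations.
- **Section 1 and section 9 (Key informant interviews).** Interviews are limited to TEE Veterans and their clinicians and take place after the intervention, with no week given. The text names who writes the interview guides, but not who schedules or conducts the interviews.

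**The concern.** The sponsor chose to blind the assessor and wrote a safeguard for it. That safeguard covers one route of unblinding, disclosure by the Veteran. The clinician invitation is a second route, and nothing in the plan covers it. A person who is handed a list of clinicians to invite, when only TEE Veterans' clinicians can qualify, has in effect been handed the TEE list.

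What is at stake is mainly follow-up. The RA schedules the assessments, and the Aim 1 hypothesis compares the arms on remaining in the study. An RA who knows that a Veteran is in TEE could, without intending to, chase that Veteran's visits harder or less hard. The pilot is also meant to show that the procedures are ready for a multi-site efficacy trial, so a gap in assessor blinding here could be carried forward.

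**Working it through.** The plan gives no figure for this point. The check sets the sections side by side and counts the Veterans who could be affected.

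1. **Is the inviter the blinded assessor?** Section 6 says research assistant, section 7 introduces the abbreviation RA, and section 9 uses it. Every reference is singular, Table 1 has one line for hiring and training an RA, and no second RA is described. I take them to be the same person.

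2. **Is anyone else named as inviter?** No. The opening of section 6 mentions flyers, clinic rounds and email, but names no role. It may also mean recruiting Veterans through their clinicians. For Veterans with a single clinician, no inviter is stated at all.

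3. **Does being invited carry information about arm?** Only if invitations are confined to clinicians who can qualify. Section 4 ties eligibility to a TEE-assigned Veteran, so somebody must know the allocation to apply it. No section says who.

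4. **When does the invitation occur?** It comes after the Veteran enrolls, with no upper limit. It must precede the interview. The intervention runs 4 weeks and the last assessment is at week 16, so if the intervention starts promptly after randomization, an interview held soon after it could fall up to 16 − 4 = 12 weeks before that assessment.

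5. **How many Veterans?** 40 randomized × 1/2 (1:1 allocation) = about 20 in TEE. If clinicians in both arms were invited, there would be up to 40 invitations at one clinician per Veteran, of whom 40 − 20 = about 20 could not qualify under section 4.

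6. **Arrangements that the text allows:**

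| Arrangement | Veterans whose TEE assignment is revealed to the RA before the last assessment | Follow-ups exposed (of 2) |
|---|---|---|
| RA invites TEE clinicians only, after randomization and before the week-4 assessment | up to about 20 | 2 |
| RA invites TEE clinicians only, between the week-4 and week-16 assessments | up to about 20 | 1 |
| RA invites both arms and also applies the TEE filter | up to about 20 | depends on when the filter is applied |
| RA invites both arms; someone else filters and the RA is not told | 0 | 0 |
| RA invites before randomization and is not told which clinicians later qualify | 0 | 0 |
| RA invites only after that Veteran's 16-week assessment | 0 | 0 |

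The count covers direct reveals. In the first two rows, the absence of an invitation would also hint at the control arm, but less surely.

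None of the last three rows is stated in the plan. The size of any resulting bias cannot be derived from the documents.

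**The case against.** The strongest reply is that the harm depends on an arrangement the protocol does not state. Section 6 speaks of Veteran participants generally, not of TEE Veterans. The requirement for one TEE session is tied to the interview, so it can be checked after the invitation. Inviting clinicians in both arms and filtering later therefore fits section 6 well. The qualitative part of section 11 also refers once to exit interviews, which could mean exit from the study and so place them near the end of follow-up. This stands as far as it goes: the text is open, and a harmless reading is available. But that reading keeps the blind only if someone other than the RA does the filtering, and exit could equally mean exit from the intervention.

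A second reply is that little would follow. The SAS-SR is a self-report, the IIP-32 and DERS are questionnaire scores, section 11 plans descriptive summaries with no between-arm test, and the investigators and coordinator review assessment completion every month. This also stands, and it is why the point is minor. It does not remove the exposure of arm-level retention, which can shift without any test being run.

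A reader might go further and infer that the RA will conduct the key informant interviews and be unblinded that way. The documents do not support this. No section links the RA to the interviews; the interviewer is simply not named.

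**Conclusion.** The concern holds as an omission. The plan declares the assessor blind, gives that assessor a task that can reveal allocation, and does not say how the task is done without revealing it. Between 0 and about 20 Veterans could be revealed, ahead of 0, 1 or 2 of the follow-up assessments.

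The severity is minor. The likely effect on self-reported scores is small; the main exposure is follow-up effort and the Aim 1 retention comparison.

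A reader might infer that sections 4, 6 and 9 contradict each other, or that the RA is bound to be unblinded. Neither follows, because several arrangements consistent with all three sections keep the blind.

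The conclusion assumes that the research assistant of section 6 is the RA of section 9, and that the RA also invites the clinicians of Veterans who have only one, for whom no inviter is named. The upper figure further assumes an even split of 40 Veterans and an invitation for every TEE Veteran.

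**What to change.** In section 6, replace the clause that gives the invitation to the research assistant with:

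*The project coordinator, who conducts randomization, will check clinician eligibility and invite the clinicians of TEE-assigned Veterans, whether the Veteran has one clinician or more; the blinded RA will not be told which clinicians are invited.*

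Where a Veteran has several clinicians, the one the Veteran identifies is still the one invited.

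In section 9, under key informant interviews, add as the same precaution:

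*The blinded RA will not schedule or conduct a Veteran's or clinician's key informant interview before that Veteran's 16-week assessment.*

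This is a cheap improvement of two sentences. About 20 invitations move to the coordinator, assuming one clinician per TEE Veteran. The coordinator needs no new access to allocation, since that role already conducts randomization. No interview hours are claimed as a cost, because the documents do not assign the interviews to the RA. If the sponsor had intended the RA to do them, someone else would have to, or they would wait until after week 16, with some loss of recall about TEE.

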Project Description

Date: 04/07/2022 Revision of Original Protocol to Adjust for Covid Pandemic

Project Title: Feasibility and Acceptability of The Equus Effect: A Small Randomized Controlled Pilot Study of an Equine-facilitated Therapy

Principal Investigator: [name].

Purpose

We propose to pilot test an innovative equine-facilitated therapy called The Equus Effect (TEE) as a complement to Veterans' existing VA mental health services to improve social functioning. TEE aims to improve Veterans' social functioning by developing their emotion regulation and interpersonal skills through therapeutic interactions with horses. In line with recommendations for pilot investigations, we will conduct a randomized pilot study to 1) evaluate the feasibility of study procedures, assessments, and outcomes, 2) demonstrate experimental and control interventions can be delivered with fidelity, and 3) examine the acceptability of the interventions. To accomplish these goals, we will enroll a transdiagnostic cohort of 40 Veterans involved in VA mental health services with social dysfunction and emotion dysregulation. We will randomize participants to receive either 1) TEE or 2) attention control (AC), both group interventions. Each week, the 4-session TEE will include 1) mindfulness activities, 2) emotion regulation and interpersonal skills education, 3) experiential activities with horses incorporating opportunities to develop emotion regulation and interpersonal skills, and 4) between-session application of lessons learned from the equine activities. AC will have similar elements without equine features. Intervention outcomes will be measured at 4- and 16-weeks post randomization. Specifically, using mixed quantitative-qualitative methods, we aim to:

Aim 1: Determine the feasibility of recruitment, randomization, retention, assessment procedures, and implementation of TEE and AC. *Hypothesis:* Rates of recruitment will be ≥ 8 participants per month, and Veterans randomized to TEE will attend intervention sessions, remain in the study, and experience clinically significant changes in social functioning and emotion dysregulation at rates equal to or superior to AC.

Aim 2: Demonstrate TEE and AC can be delivered with fidelity. *Hypothesis:* Facilitators will deliver each intervention consistently and as intended across sessions.

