The proposed pilot study will advance knowledge in rehabilitation research by studying the feasibility and acceptability of conducting a randomized controlled trial of an EFT, called The Equus Effect (TEE), currently available to Veterans at VA Connecticut Healthcare System (VACHS). TEE is a 4-session intervention that incorporates mindfulness strategies, emotion regulation and interpersonal skill development, and experiential equine activities to improve social functioning for a mixed diagnostic group of Veterans. Data from the pilot study will inform development of a RR&D IIR proposal testing the efficacy of TEE in a multi-site randomized controlled trial. The proposed research aligns with the RR&D SPiRE Program Priority Areas for studying

promising non-pharmacological activity-based interventions to maximize functional recovery,²⁵ OPCC&CT promotion of CIH within the Whole Health initiative,¹ and the VA 2018-2024 Strategic Plan to ensure Veterans receive integrated care and support that emphasizes their well-being and independence.²⁶

Research Plan

1. Study design and overview. We will test the feasibility and acceptability of a randomized controlled trial design to study TEE to improve social functioning. We will enroll a transdiagnostic cohort of 40 Veterans with social dysfunction and emotion dysregulation who are receiving VA mental health services and randomize them to either weekly TEE or attention control (AC) sessions over 4 weeks. Social functioning will serve as the primary outcome; emotion dysregulation will serve as the secondary outcome. Following best practice recommendations for pilot investigations,^{27,28} we will use mixed quantitative and qualitative methods. Feasibility will examine performance of study procedures, assessment measures, and outcomes (Aim 1) and fidelity of TEE and AC (Aim 2). Acceptability will involve assessing TEE and AC credibility and satisfaction, as well as conducting key informant interviews with Veterans assigned to TEE and their clinicians (n = 20) to examine perceptions of the acceptability and usefulness of TEE and the ways in which it complements standard mental health care (Aim 3). Intervention outcomes will be measured at baseline and 4- and 16-weeks post-randomization.

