If VA DocuSign is infeasible to use with potential participants, the consent form will be mailed to subjects after participating in the phone screening to determine initial eligibility. Upon receipt of the consent form, another remote encounter will occur with the potential participant to review it, and have it signed and returned to the research team, if the Veteran remains interested. Once received, a member of the research team will meet remotely again with the participant to complete the screening, determine eligibility, and, if found eligible, have the participant finish the remaining baseline assessments. Remote sessions will not be recorded.

8. Intervention conditions. Veterans will receive either TEE or AC, both closed group programs in which all members begin the group intervention at the same time. TEE and AC each will consist of four 4-hour weekly sessions over 4-weeks, with 4-6 Veterans attending per 4-week cycle. Activities in both conditions contain a mixture of indoor and outdoor activities; group facilitators and participants will wear 2-ply face masks indoors or outdoors as dictated by prevailing VACHS guidelines. Masks will be provided to participants who do not have them. [name] and [name], LCSW will conduct TEE sessions. They are Experiential Learning with Horses Instructors who trained at the Epona Equestrian Services Program in Tucson, AZ – an internationally acclaimed equine educational program that trains people in EFT. They have worked together for the past decade developing and delivering TEE to Veterans. Peer specialists from VACHS or staff from the facility in Sharon, CT not delivering TEE will conduct AC sessions. They have experience facilitating general support groups and will be trained by [name] to deliver the control intervention.

TEE. Each session includes: 1) mindfulness-based activities; 2) didactics about emotion regulation and interpersonal skills; and 3) experiential learning activities with horses that provide opportunities to practice emotion regulation and interpersonal skills. At the end of each session, Veterans debrief about what they learned and identify how they might apply this knowledge to manage their mental health concerns and function better socially. [name] and [name] have prepared a manual detailing the program’s major components and content and will co-facilitate its delivery to participants in this pilot study.

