AC. AC will exclude equine-related activities or discussions but maintain mindfulness-based activities, emotion regulation and interpersonal skills didactics, and experiential learning activities with between-session application. During the first five months of the study, Drs. [name], [name], and [name] will develop and manualize AC to parallel the focus, content, and activities of TEE. Instead of experiential equine activities, AC will rely on team-building activities (e.g., scavenger hunt), which aim to enhance social relations by involving participants in collaborative tasks and providing opportunities for emotion regulation and interpersonal skills practice.²⁹ Group leaders will practice the finalized curriculum with the research team in month 5 and then co-facilitate it for Veterans randomized to this condition.

TEE will occur at the horse stables and pastures/ring where the program occurs in Sharon, CT. AC will occur at a cottage on the same property, but not in the stables and pastures/ring. Table 2 compares TEE and AC sessions. All TEE and AC sessions will be audio recorded, except for the experiential equine activities because of excessive logistical challenges.

Veterans will have the choice to be transported by van to and from the intervention location by the Peer Specialists from VACHS or the Disabled American Veterans Department of Connecticut. If they choose to use van transportation provided for this study, they will first be screened by the driver for symptoms that could be consistent with COVID-19 infection. Participants will only be permitted to enter the vehicle if they pass symptom screening. During the drive, they will always wear 2-ply masks, which will be provided to those who do not have one. They will not be allowed to eat or drink while in the vehicle, and weather permitting, windows will be slightly open to allow for air circulation. COVID-19 risk mitigation procedures for travel will be adjusted according to prevailing VACHS guidelines.

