Rationale for AC. For most Veterans, interacting with horses will be an unusual experience, and driving to the countryside and spending four hours in a bucolic setting may confer therapeutic benefits (e.g., stress reduction). Replicating TEE without horse-specific components will be essential to determine therapeutic gains specific to equine interactions. We elected not to include interactions with another large, familiar animal (e.g., a cow) as a more stringent test of “the equus effect” because of its impracticality, uncommonness as a

social/recreational activity, and the possibility that other animals could elicit different responses from different people (e.g., fear/hesitation vs. attraction/approach), making interpretation of potential condition differences difficult.

Table 2. TEE vs. AC.

		Content/Activities	
Session	Focus	TEE	AC (manual to be developed)
1	Mindfulness	Joint fluidity/body scan in horse barn	Joint fluidity/body scan in cottage
	Emotion regulation & interpersonal skills	Fear and vulnerability/video, discussion w/ parallels to horses	Fear and vulnerability; video, discussion; no horse parallels
	Experiential learning activity	Setting healthy boundaries/grooming, leading, yielding, backing up with horse	Team building activity requiring disclosure and boundary management
2	Mindfulness	Joint fluidity/body scan in horse barn	Joint fluidity/body scan in cottage
	Emotion regulation & interpersonal skills	Anger/Frustration/Agitation; video, discussion w/ parallels to horses	Anger/Frustration/Agitation; video, discussion; no horse parallels
	Experiential learning activity	Collaboration/ grooming, obstacle course with horse	Team building activity requiring collaboration
3	Mindfulness	Joint fluidity/body scan in horse barn	Joint fluidity/body scan in cottage
	Emotion regulation & interpersonal skills	Sadness and Grief; video, discussion w/ parallels to horses	Sadness and Grief; video, discussion; no horse parallels
	Experiential learning activity	Collaboration/ grooming, walk through labyrinth or trail with horse	Team building activity requiring collaboration
4	Mindfulness	Joint fluidity/body scan in horse barn	Joint fluidity/body scan in cottage
	Emotion regulation & interpersonal skills	Review of emotional states; video, discussion w/ parallels to horses	Review of emotional states; video, discussion; no horse parallels

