Key informant interviews. Key informant individual 20/30-minute interviews will take place post-intervention to assess Veteran and clinician perceptions of the acceptability, usefulness, and satisfaction of TEE. Drs. [name], [name], and [name], and [name] and [name] will develop the Veteran and clinician interview guides to ensure questions and probes ascertain main topics. These interviews will be audio recorded using either Microsoft TEAMS (from a VA desktop or laptop) or a VA-approved audio recorder. Microsoft TEAMS is a HIPAA-compliant, VA approved platform for video conferencing and has transcription generating capacity. We will also gather some demographic and professional characteristics of clinician participants (i.e., age, sex, race/ethnicity, profession/discipline, professional status (e.g., staff, trainee), Veteran status, months treating Veteran, years providing clinical services, and major focus of mental health service provided to Veteran) to characterize the sample.

10. Data management. Quantitative assessment measure responses will be entered into VA REDCap to provide secure automated export procedures for data to be downloaded to Excel and common statistical packages (e.g., SAS) for data analysis. REDCap catches unclear characters, out-of-range variable and logical inconsistencies. The research assistant will check files monthly so that errors can be readily corrected.

11. Data analysis.

Quantitative. To assess feasibility (Aim 1), we will use CONSORT reporting standards to diagram the number of Veterans screened, found eligible and ineligible (with reasons), consented, attended sessions, completed TEE and AC interventions, and retained through follow-up. We also will track rates of unanticipated study-related adverse events in both conditions and participants' rate of completion of all outcome measures. Means, standard deviations, and median scores will be calculated for outcome assessments. The proportions of participants with clinically significant change in outcomes from baseline to 4- and 16-weeks post-randomization will be calculated using each measure's test-retest reliability and clinical cutoffs from the literature, or change of two standard deviations from the baseline mean when clinical cut-offs are not available.⁴⁵ To assess intervention fidelity (Aim 2), we will determine the proportion of sessions that contain all

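### The planned adverse-event rate covers only events that are both unanticipated and study-related, so a zero would bound that category alone and say nothing about other harms

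*Combined protocol and SAP*

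**What the plan says.** Section 11 (Data analysis, Quantitative) states under Aim 1: "We also will track rates of unanticipated study-related adverse events in both conditions". The term adverse events appears nowhere else in the document. The document does not define either qualifier, say who applies them, or give a collection method, time window or denominator.

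The two arms differ in exposure to horses. Section 8 says "AC will exclude equine-related activities or discussions". Table 2 shows horse work in all four TEE sessions, beginning with "grooming, leading, yielding, backing up with horse". The control arm does team-building tasks instead, in a cottage on the same property.

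Section 6 lists what goes to the Data Safety Monitoring Board: screening, eligibility, refusal, randomization, start, completion, withdrawal and assessment numbers. Adverse events are not in that list.

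**The concern.** The two qualifiers act together as a filter on what is reported. An event must be both unexpected and attributable to the study to count. The harms most specific to TEE are physical ones from handling a large animal, and these are easy to foresee. The Background section itself says that in this type of therapy a horse specialist typically looks after participants' physical safety. If such an injury were classed as anticipated, it would drop out of the rate in the only arm where it can occur.

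The pilot is meant to inform a multi-site efficacy trial. That trial's planners need a plain description of how many participants were harmed, how seriously, and in which arm. Under the current sentence they could receive a low or zero rate without knowing what lay outside it.

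**Working it through.** **Step 1: does another section supply a broader count?**

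- *Section 11, CONSORT.* It is invoked to diagram participant flow, not to tabulate harms.
- *Section 6, board reports.* Recruitment and retention numbers only.
- *Section 9, Outcomes.* Psychiatric symptoms, PTSD symptoms and pain are measured in both arms, but as scores. There is a response pathway for suicidal ideation, without a count.
- *Section 9, Intervention Fidelity.* Facilitator checklists document adherence to the prescribed activities.
- *Section 8, recordings.* "All TEE and AC sessions will be audio recorded, except for the experiential equine activities because of excessive logistical challenges". The exception covers the equine activities only. The debrief falls outside it ("At the end of each session, Veterans debrief about what they learned"), so a recording might mention an event, but no count from recordings is planned.
- *Section 1, key informant interviews.* These involve only Veterans assigned to TEE and their clinicians, so they give no control-arm comparison.

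None of these is a count of adverse events by arm.

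**Step 2: what does a zero bound?** The plan gives no harm rate, so there is no figure to reproduce.

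Inputs: 40 Veterans (section 1) randomized 1:1 (section 5), taken as 20 per arm. For zero events among n participants, the exact (Clopper-Pearson) two-sided 95% upper limit is 1 − 0.025^(1/n).

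- n = 20: 1 − 0.025^(1/20) = 16.8%
- n = 18: 18.5%
- n = 22: 15.4%

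The last two cover slightly unequal arms. In each case the limit applies only to unanticipated study-related events.

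**Step 3: what could lie outside it?** Suppose some TEE participants had only events classed as anticipated or unrelated, and nobody had a counted event. These counts are illustrations, not predictions.

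| TEE participants with any event | Planned rate (exact 95% CI) | All-event proportion (exact 95% CI) |
|---|---|---|
| 1 | 0/20 (0 to 16.8%) | 1/20 = 5% (0.1 to 24.9%) |
| 2 | 0/20 (0 to 16.8%) | 2/20 = 10% (1.2 to 31.7%) |
| 4 | 0/20 (0 to 16.8%) | 4/20 = 20% (5.7 to 43.7%) |

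The planned result is the same in every row. The intervals treat participants as independent. Delivery in groups of 4-6 (section 8) could make the correct intervals wider.

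**Step 4: what depends on the rate?** The Aim 1 hypothesis concerns a recruitment rate and that "Veterans randomized to TEE will attend intervention sessions, remain in the study, and experience clinically significant changes in social functioning and emotion dysregulation" at rates at least equal to control. Adverse events are not part of it, and no stated progression rule uses them.

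**The case against.** The strongest case on the other side has five parts.

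*A reader might infer that a zero would be meaningless.* The documents do not support that. A 0/20 bounds the stated category at 16.8%. What it does not do is bound anything outside the category.

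*A reader might infer that other events will go unrecorded.* The sentence does not say so. It governs the reported rate, and staff must learn of an event before they can classify it. The filter is on reporting; collection is simply not described.

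*A reader might infer that handling injuries are hidden, or that no wider safety count exists anywhere.* Neither is established. No section classes such an injury either way. Consent pages, which may list risks, are not in the public text. The study has ethics review and a monitoring board, and a separate safety plan could say more, although none is cited. The claim is therefore about what this document states, and the injury example is conditional on the classification.

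*Other data give context.* Symptom and pain scores in both arms, together with withdrawal numbers, would help a reader judge psychological worsening in particular. That is true, but they are not event counts and would not capture an injury as such.

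*The arithmetic would hold for any subset in any trial.* It would, and it does not show that an undercount is likely or large here. It shows only that the 16.8% limit cannot be carried over to harm overall.

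What stands is that the filter is stated and that no broader count is stated beside it.

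**Conclusion.** The point holds in limited form. As written, the plan reports by arm only events that are both unanticipated and study-related, and it states no count of all, serious, or anticipated study-related events. Following it exactly could leave foreseeable horse-handling injuries out of the TEE rate if they are classed as anticipated.

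With 20 per arm assumed, a zero would carry an upper limit of 16.8% for the narrow category and no information about the rest. The size of any undercount cannot be estimated, because the document gives neither a harm rate nor a classification rule.

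Feasibility conclusions do not turn on this rate, so the damage is confined to the harm description passed to the multi-site trial. It should be fixed because the remedy is cheap and events not recorded during the trial may not be recoverable later.

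**What to change.** Replace the adverse-event sentence in section 11 with:

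> All adverse events from randomization to 16 weeks will be recorded in the same way in both conditions, with seriousness, expectedness and relatedness recorded as attributes rather than used as filters. The number and proportion of participants with at least one event will be reported by arm with exact 95% CIs, with serious, study-related, and unanticipated study-related events as subsets.

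Name the role that classifies events, and add these counts to the existing board reports in section 6.

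Collect events without unblinding the research assistant, who is blind to condition under section 9. For example, facilitators in both arms could complete a short form alongside the weekly checklist, and the project coordinator could ask one standard question after the 4- and 16-week outcome measures are finished.

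**Cost.** Section 6 plans 8-12 Veterans per cycle, so 40 Veterans need 4-5 cycles (40/12 = 3.3, rounded up to 4; 40/8 = 5). With two groups and four sessions per cycle, that is 4 × 2 × 4 = 32 to 5 × 2 × 4 = 40 group-session forms. One form per participant per session would be up to 40 × 4 = 160. Follow-up questions add up to 40 × 2 = 80. The maxima assume full attendance and retention.

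Ascertainment would not be blinded, and this should be stated as a limitation. Facilitators know the arm, the coordinator conducts randomization (section 5), and of the TEE facilitators section 8 says "They have worked together for the past decade developing and delivering TEE to Veterans". The reported rate may also look less favourable. Nothing planned is lost, since the current category remains as a subset.
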